## 2.4 Endpoints

### 2.4.1 Primary Endpoint

ORR is defined as the percentage of subjects with unresectable refractory *KRAS/NRAS/BRAF* wild-type MSS mCRC who achieve a complete response or a partial response (CR+PR) by 12 weeks to panitumumab/nivolumab/ipilimumab or panitumumab/nivolumab therapy per RECIST 1.1 criteria.

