### 2.4.2 Secondary Endpoints

**2.4.2.1** The best overall responses for both RECIST 1.1 and irRECIST are defined as the best response achieved across all time points prior to progression (for example, a subject who has SD at first assessment, PR at second assessment, and PD on last assessment has a best overall response of PR). Please Note: In the case of SD, measurements must have met the SD criteria at least once after study entry at a minimum interval of 12 weeks from initiation of treatment.

**2.4.2.2** The immune-related response rate is defined as the percentage of subjects with unresectable refractory *KRAS/NRAS/BRAF* wild-type MSS mCRC who achieve a CR+PR by 12 weeks to panitumumab/nivolumab/ipilimumab or panitumumab/nivolumab therapy per irRECIST criteria. (See section 6.7.5.1)

**2.4.2.3** Assessment of immune-related PFS is defined as starting from the first day of treatment or Day 1 (D1) until the event of disease progression as defined by irRECIST, or death from any cause in subjects with unresectable refractory *KRAS/NRAS/BRAF* wild-type MSS mCRC (See section 6.7.5.1). Any subject that has not had a documented event at the time of analysis will be censored. Assessment of PFS (as defined by RECIST 1.1) is defined from D1 of treatment until the event of disease progression occurs or death from any cause in subjects with unresectable refractory *KRAS/NRAS/BRAF* wild-type MSS mCRC. Any

October 01,,  
2020

subject that has not had a documented event at the time of analysis will be censored.

- 2.4.2.4 OS is defined as the time from D1 of treatment until death from any cause. Any subject that has not died by the analysis date will be censored.
- 2.4.2.5 The duration of response as defined by RECIST 1.1 will be defined as the time elapsed from first scan documenting partial response or complete response until the event of disease progression occurs. Any subject that has not had a documented progression at the time of analysis will be censored. The duration of response as defined by irRECIST will be defined as the time elapsed from first scan documenting partial response or complete response until the event of disease progression occurs. Any subject that has not had a documented progression at the time of analysis will be censored.
- 2.4.2.6 Treatment-related adverse events will be assessed per NCI-CTCAE v4.03.

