
If DLTs occur in no more than one subject in the first 6 subjects treated during the 12 week assessment period in the first safety cohort, then the trial would continue enrolling subjects to the remainder of the first stage of the phase II portion to complete enrollment to 32 subjects to assess efficacy of panitumumab, ipilimumab and nivolumab (3-drug combination). This would then be followed by interim analysis to determine whether the second stage would merit enrollment. If the 3-drug combination is not well tolerated, then 6 additional subjects will be enrolled into safety cohort 2 and receive panitumumab and nivolumab (2-drug combination). If no more than one subject experiences a DLT in safety cohort 2, then the trial will continue enrolling subjects into the phase II portion and the 2-

October 01,,  
2020

drug combination of panitumumab and nivolumab will be evaluated efficacy. Subjects may continue combination treatment as long as they are benefitting from therapy until disease progression, unacceptable toxicity or withdrawal for other reasons as deemed necessary by the investigator.

DLT definitions applicable to the safety assessment run-in are defined in section 4.2. Subjects will undergo disease evaluation every 6 weeks for the first year, and will continue on this disease assessment schedule if they are at least stable but have less than a CR. If subjects continue on study after one year with a CR, then disease evaluations may occur every 12 weeks from that point forward.

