3. The end of treatment visit should only occur when subjects permanently stop study treatment. Subjects who have an ongoing  $\geq$  grade 2 or serious AE (SAE) at this visit will continue to be followed until the event is resolved or deemed irreversible by the investigator. The 30-day (+/- 7 days) follow up visit after stopping study treatment should be performed to check for ongoing toxicity. Subsequently, subjects should be contacted by telephone at approximately 100 days (+/- 7 days) after discontinuing study treatment for the emergence of SAEs (including checking for pregnancy) and to ensure contraceptive guidelines are followed as stipulated in inclusion criteria 3.1.11 and 3.1.12. Subsequent long-term follow-up for survival, defined as every 90 days thereafter (+/- 15 days) for up to 3 years or until death (whichever is first) may be conducted via telephone or chart review and/or clinic visit. Long term survival follow up will be limited to history of any subsequent cancer treatments, an assessment of any SAEs (including checking for pregnancy) considered to be possibly or probably related to study treatment until resolution, and survival status.
4. Complete history at baseline only, thereafter focused history on symptoms/toxicity; physical exam to include height (baseline only), examination of the skin, weight, and vital signs. Note that starting with cycle 7, only include assessment by physician on days 15 and 29 if clinical signs and symptoms warrant MD consult
5. Tumor imaging should remain consistent throughout study and should include those thought by investigator to best capture status of disease. Disease assessments should include contrasted computed tomography (CT) of the chest and either contrasted CT of abdomen and pelvis or MRI of abdomen and pelvis. Repeat tumor imaging every 12 weeks (+/- 1 week).
6. Urine or serum  $\beta$ -HCG must be performed within 24 hours prior to first dose of study medication for women of child-bearing potential. The test result must be confirmed as negative prior to dosing with study medication. A serum or urine pregnancy test must be repeated every 6 weeks while receiving study medications and repeated approximately 30 days after discontinuing the study medications.

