#### 6.3.5 D1 of Cycle 3-N

Focused history and physical examination (including weight) /

ECOG Performance Status (see appendix 11.1)

Laboratory evaluations:

- Hematology: CBC with differential
- Complete Metabolic Panel (plus Mg and Phosphorus)
- TSH/Free T3/Free T4
- ACTH/Amylase/Lipase
- CEA
- Serum or urine pregnancy test in women of childbearing potential (within 24 hours of dosing with study medications)
- Blood sample for correlative studies

Concomitant medication(s): All concomitant medications will be recorded.

Tumor evaluation: Contrasted computed tomography (CT) of the chest, and either contrasted CT of abdomen and pelvis or MRI of abdomen and pelvis on cycles 3, 5, 7, etc. **Note:** Repeat tumor imaging every 12 weeks (+/- 1 week).

Stool Specimen: Collect stool specimen from patients as described in Laboratory manual +/- 7 days from Day 1 of Cycle 3 only.

Toxicity evaluation: Use NCI CTCAEv4.03 for notation of any baseline toxicity

Administer Study Medications according to Safety Cohort 1 or 2 schedule as depicted in sections 4.3.10 and 4.3.2, respectively

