**6.7.5 Other Efficacy Parameters (Immune Response Criteria)**

**6.7.5.1 Evaluation of Response by irRECIST**

Secondary objectives of this study involve assessment of ORR and PFS based in immune response criteria as outlined below (see Guidelines for the evaluation of immune therapy activity in solid tumors: immune-related response criteria. Wolchok JD et al. Clin Cancer Res 2009;15(23):7412-20, Nishino et al. Clin Cancer Res 19(14):3936-43, and Bohnsack O. et al., *Adaptation of the immune related response criteria: irRECIST*. Annals of Oncology (2014) 25 (suppl\_4): iv361-iv372. 10.1093/annonc/mdu342, 2014).

irRECIST criteria are based on irRC criteria (Wolchok et al) adapted for unidimensional measurement as outlined by Nishino et al. The adaptation described by Bohnsack et al. further aligns irRECIST to allow for assessment of

baseline non-target lesions and new non-measurable lesions and discusses the impact of those lesions on the overall tumor response assessment. The adaptation by Bohnsack et al. allows for evaluation of subjects with non-target disease only and subjects in the adjuvant setting (not applicable for this study in subjects with metastatic disease).

Overall response using the irRECIST is based on tumor burden as follows:

irCR	Complete disappearance of all lesions (whether measurable or not, and no new lesions) Lymph nodes must decrease to < 10 mm in short axis. Confirmation of response is not mandatory.
irPR	Decrease in tumor burden $\geq 30\%$ in TMTB relative to baseline confirmed by a consecutive assessment at least 4 weeks after first documentation, non-target lesions are irNN, and no equivocal progression of new non-measurable lesions.
irSD	Not meeting criteria for irCR, irPR, in absence of irPD
irPD	Increase in tumor burden $\geq 20\%$ increase and minimum 5 mm absolute increase in TMTB compared to nadir, or irPD for non-target or new non-measurable lesions confirmed by a repeat, consecutive assessment no less than 4 weeks from the date first documented
irNN	No target disease was identified at baseline and at follow-up the subject fails to meet criteria for irCR or irPD.

irNN = irNon-CR/Non-PD

TMTB = Total measurable tumor burden

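### Section 4.1.1 sets tumor assessment every 6 weeks in the first year; 6.1 and 6.3.5 set it every 12 weeks from the start; no text says which governs

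*Combined protocol and SAP*

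**What the plan says.** Two places in the current text set the interval differently.

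- **Section 4.1.1**, last paragraph: "Subjects will undergo disease evaluation every 6 weeks for the first year, and will continue on this disease assessment schedule". The continuation applies to subjects with stable disease or better who have not reached a CR. The next sentence adds: "If subjects continue on study after one year with a CR, then disease evaluations may occur every 12 weeks from that point forward".
- **Section 6.1, footnote 5**: "Repeat tumor imaging every 12 weeks (+/- 1 week"), with no condition on year or response. Section 6.3.5 repeats this rule and places the scans as "MRI of abdomen and pelvis on cycles 3, 5, 7, etc". The tumor-measurement row of the 6.1 table is marked at pre-study and at Day 1 of Cycle 3 onward, not at Cycle 2 Day 1. Section 6.3.4, which lists the Cycle 2 Day 1 procedures, has no tumor evaluation.

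These endpoint definitions depend on scan timing:

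- Primary ORR (2.4.1): "a complete response or a partial response (CR+PR) by 12 weeks" by RECIST 1.1. Sections 2.1 and 8.1 say *at* 12 weeks rather than *by*.
- irRECIST response rate (2.4.2.2): subjects who "achieve a CR+PR by 12 weeks to panitumumab/nivolumab/ipilimumab or panitumumab/nivolumab therapy per irRECIST criteria".
- irPR (6.7.5.1): the decrease must be "confirmed by a consecutive assessment at least 4 weeks after first documentation". An irCR needs no confirmation.
- PFS and duration of response (2.4.2.3, 2.4.2.5): both run to documented progression, by RECIST 1.1 and by irRECIST.

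**The concern.** The two texts describe one procedure. Section 4.1.1 calls it the disease assessment schedule, and footnote 5 defines what that means: "Disease assessments should include contrasted computed tomography (CT) of the chest" plus CT or MRI of the abdomen and pelvis. Nor is the 6 likely to be a slip for 12, because 4.1.1 contrasts the two intervals in consecutive sentences; if both were 12, the relaxation after a year with a CR would change nothing.

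The first on-treatment scan is therefore due on Day 43 or on Day 85, depending on which section a site reads. In a multicenter trial, sites can differ. Two sets of secondary results are exposed: the time-to-progression endpoints, whose recorded dates depend on when a scan is taken, and the 12-week irRECIST response rate, which needs a second scan to confirm a partial response.

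**Working it through.** **1. Calendar.** Inputs: cycle length 42 days (6.1, footnote 2), with Cycle 1 Day 1 as D1. Day 1 of cycle c falls on D[1 + 42 × (c − 1)].

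Cycles 3, 5, 7 and 9 start on D85, D169, D253 and D337, which are 84, 168, 252 and 336 days, or 12, 24, 36 and 48 weeks, after D1. So the cycle label in 6.3.5 reproduces the 12-week rule when there are no delays. It does not reproduce the 6-week rule, which would need a scan at every cycle start from Cycle 2.

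| | 6-weekly (4.1.1) | 12-weekly (6.1, 6.3.5) |
|---|---|---|
| First scan | D43 | D85 (window D78 to D92) |
| Scans by week 12 | 2 | 1 |
| Scans by week 52 | 8 | 4 |

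Both columns contain the week-12 scan (D85).

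**2. Confirming an irPR by week 12.** Rule: confirmation day ≥ first day seen + 28.

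- 6-weekly: seen on D43, confirmable from 43 + 28 = D71, so the D85 scan confirms it. An irPR first seen on D85 can be confirmed no earlier than 85 + 28 = D113.
- 12-weekly: seen at the earliest on D78, confirmable from 78 + 28 = D106. That is after week 12 and also after the end of the scan window (D92). The next scheduled scan is 169 ± 7, or D162 to D176.

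If confirmation must also fall by week 12, 12-weekly scans allow no irPR to count, only an irCR. Six-weekly scans allow only an irPR already present at week 6. No text says whether later confirmation counts.

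**3. Median PFS.** The documents give no expected PFS, so these are assumptions: exponential progression times T, true median 3 to 6 months, n = 56, every event found by scan, no censoring. Observed time = I × ceil(T / I), with I = 6 or 12 weeks. Averages of the observed median over 20,000 simulated trials:

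| True median | 6-weekly | 12-weekly | Difference |
|---|---|---|---|
| 3 months (13.0 wk) | 15.9 wk | 19.4 wk | 3.5 wk |
| 4 months (17.4 wk) | 20.2 wk | 23.8 wk | 3.6 wk |
| 5 months (21.7 wk) | 24.5 wk | 27.1 wk | 2.6 wk |
| 6 months (26.1 wk) | 28.7 wk | 31.7 wk | 3.0 wk |

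At medians between these the difference reaches about 4.2 weeks. The mean delay from true to detected progression is about 3.1 weeks with 6-weekly scans and 6.3 to 6.6 weeks with 12-weekly scans, close to half the interval in each case.

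**4. Duration of response.** This also depends on the schedule, but the direction is not fixed: sparser scans date both the first response and the progression later. No size is claimed.

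**The case against.** The best defense is that every operational part of the protocol agrees on 12 weeks: the 6.1 table, footnote 5, 6.3.5, and the stool sample, which 1.6 ties to first restaging and 6.1 and 6.5 place at Cycle 3 Day 1. The outlier is two sentences at the end of a dose-rationale section. Nothing shows that any site scanned every 6 weeks, and PFS and duration of response are descriptive Kaplan-Meier estimates with no hypothesis test (8.4). This stands as evidence of intent and keeps the point in proportion. It does not settle the matter, because no text gives the table precedence.

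It is also fair that the irPR problem is partly separate. An irPR first seen at D85 cannot be confirmed by week 12 on either schedule, so choosing an interval alone does not resolve it.

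A reader might draw three stronger conclusions that the documents do not support:

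- *The primary result changes.* A PR seen at week 6 and lost by week 12 would count only if the week-6 scan existed and 2.4.1 (*by*) prevailed over 2.1 and 8.1 (*at*). The best-response table in 6.7.4.1 scores PR then SD as SD, while the worked example above it points the other way. That is a separate ambiguity.
- *Subjects who progress early receive all of cycle 2 because of the later scan.* Sections 4.6 and 6.7.4 already continue treatment in asymptomatic subjects, at the physician's discretion, until a repeat scan about 4 to 6 weeks after progression. Much of cycle 2 would usually be given under either schedule.
- *The cycle label lets scans drift after dose delays.* Section 6.3.5 prints the 12-week rule beside the label, and 4.4.2.5 keeps tumor assessments going when dosing is interrupted. At most this is a small gap, because no clock is named.

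**Conclusion.** The inconsistency is real, is in operative text, and is worth correcting. Twelve weeks is probably what was meant, but the sponsor must confirm it. The sample size and two-stage design are unaffected, and the primary ORR can be measured under either schedule.

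The effect falls on secondary endpoints. Observed median PFS would average about 2.5 to 4 weeks longer under 12-weekly than under 6-weekly scans. That rests on exponential times, an assumed true median of 3 to 6 months, and every event being found by scan; deaths before a scan, or censoring, would alter it. The irRECIST conclusion needs only calendar arithmetic and scheduled scans: under the 12-week schedule no irPR can be both seen and confirmed by week 12, and under the 6-week schedule only one present at week 6 can be.

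**What to change.** **If 12 weeks is intended (the smaller edit).** Replace the two sentences in 4.1.1 with: *Tumor imaging (6.1 footnote 5) is done every 12 weeks (+/- 1 week) counted from C1D1 and is not moved when doses are delayed.* This matches the table, footnote 5, 6.3.5 and the stool timing.

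**If 6 weeks is intended.** Change footnote 5 and 6.3.5, and add a scan at Cycle 2 Day 1 to the table and to 6.3.4. The stool timing would then need rewording, since first restaging would no longer be Cycle 3 Day 1.

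**In either case**, add to 2.4.2.2: *An irPR first seen by the week-12 scan counts if confirmed at least 4 weeks later.* If sites have already used both schedules, report actual scan dates with the PFS results.

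**Cost.** With 12 weeks: text edits in 4.1.1 and 2.4.2.2. The regular week-24 scan can confirm an irPR first seen at week 12, so no extra scan is required, though that subject's irRECIST status is then settled only at D162 to D176. With 6 weeks: up to 8 − 4 = 4 more scans per subject in the first year.

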#### 4.2 Dose Limiting Toxicities for Safety Lead-in

The safety lead-in DLT assessment period is defined as the first 12 weeks (84 days) of ipilimumab/nivolumab/panitumumab therapy. An event will be considered a DLT if it occurs within the first 84 days of combination therapy and meets one of the following criteria.

- Grade 4 neutropenia lasting  $\geq 5$  days
- Febrile neutropenia
- Grade 4 thrombocytopenia
- Grade 4 anemia
- Grade 2 drug-related uveitis that does not respond to topical therapy and does not improve to Grade 1 severity within 6 weeks OR requires systemic treatment
- Grade 3 drug-related uveitis
- Grade 3-4 pneumonitis
- Grade 3-4 bronchospasm
- Grade 3-4 diarrhea
- Grade 3-4 colitis
- Grade 3-4 neurologic adverse event
- Grade 3-4 adrenal insufficiency
- Grade 3-4 hypersensitivity reaction
- Grade 3-4 infusion reaction of any duration
- Grade 3 non-skin, drug-related non-hematologic toxicity per NCI-CTCAE criteria 4.03 lasting over 7 days
- Grade 4 non-hematologic toxicity per NCI-CTCAE criteria 4.03 (excluding alopecia, isolated electrolyte disturbances that responds to correction within 72 hours of onset, isolated amylase or lipase abnormalities that are not associated with symptoms or clinical signs of pancreatitis and decrease to  $<$  Grade 4 within 1 week of onset)

### 4.3 Treatment Dosage and Administration

Dosing should be based on the subject's baseline weight on day 1 of cycle 1, as measured according to institutional standards; doses will be adjusted for subjects who experience a  $\geq 10\%$  change in weight during the study.

#### 4.3.1 Safety Cohort 1 Schedule (3-drug combination)

REGIMEN DESCRIPTION – Safety Cohort 1 )					
Agent	Premedications; Precautions	Dose/Frequency	Route	Schedule	Cycle Length
Panitumumab	See Section 4.5 and 4.5.1	6mg/kg every 2 weeks	IV (specific details below)	D1, D15, D29 of each cycle	
		For doses $\leq 1000$ mg	IV over 60 ( $\pm 15$ ) minutes		
		For doses $>1000$ mg,	IV over 90 ( $\pm 15$ ) minutes		
Ipilimumab	See Section 4.5.3	1 mg/kg every 6 weeks	IV over 30 ( $\pm 15$ ) minutes	D1 of each cycle	
Nivolumab	See sections 4.5.2 and 4.5.3	240 mg every 2 weeks	IV over 30 ( $\pm 15$ ) minutes	D1, D15, D29 of each cycle	

#### 4.3.2 Safety Cohort-2 Schedule (2-drug combination)

REGIMEN DESCRIPTION – Safety Cohort 2					
Agent	Premedications; Precautions	Dose/Frequency	Route	Schedule	Cycle Length
Panitumumab	See Section 4.5 and 4.5.1	6mg/kg every 2 weeks	IV (specific details below)	D1, D15, D29 of each cycle	
		For doses $\leq 1000$ mg,	IV over 60 ( $\pm 15$ ) minutes		
		For doses $>1000$ mg,	IV over 90 ( $\pm 15$ ) minutes		
Nivolumab	See section 4.5.2	240 mg every 2 weeks	IV over 30 ( $\pm 15$ ) minutes	D1, D15, D29 of each cycle	

If the 3-drug combination is not tolerated in Cohort 1, then ipilimumab will be omitted and panitumumab in combination with nivolumab will be evaluated for safety. If no more than 1 subject out of 6 experiences DLTs after 12 weeks on therapy, then additional subjects will be enrolled to evaluate the safety and efficacy of panitumumab and nivolumab (2-drug combination). If neither the 3-drug or 2-drug combination is well-tolerated, the dosing approach for these agents will be reconsidered.

#### 4.4 Toxicities and Dosing Delays/Dose Modifications

##### 4.4.1 Panitumumab Dosing Delays/Dose Modifications

Toxicity grades per NCI-CTCAE Criteria v 4.03

Adverse Reaction	Severity	Dose Modification
Infusion-related reactions	Grade 1 or 2	Reduce infusion rate by 50%
	Grade 3 or 4	
 
• Terminate the infusion
 
• Depending on the severity and /or persistence of the reaction, permanently discontinue panitumumab
 

Dermatologic reaction	Grade 3 – 1st occurrence	Withhold 1 or 2 doses of Panitumumab, if reaction improves to < grade 3, reinitiate at original dose
	Grade 3 – 2 nd occurrence	Withhold 1 or 2 doses of Panitumumab, if reaction improves to < grade 3, reinitiate at 80% of the original dose
	Grade 3 – 3rd occurrence	Withhold 2 doses of panitumumab, if reaction improves to < grade 3, reinitiate at 80% of the original dose
	Grade 3 - 4 th occurrence	Permanently discontinue panitumumab
	Grade 3 reaction that not recover after withholding 1 or 2 doses OR Grade 4	Permanently discontinue panitumumab
Pulmonary Fibrosis/ILD	Acute onset of pulmonary symptoms	Interrupt panitumumab until resolution
	ILD confirmed	Permanently discontinue panitumumab
Ocular toxicities	Acute or ulcerative keratitis	Interrupt panitumumab or permanently discontinue panitumumab for acute or worsening keratitis
Warnings		
Electrolyte depletion/Monitoring	Monitor subjects for hypomagnesemia and hypocalcemia prior to initiating panitumumab and periodically during panitumumab treatment, and for up to 8 weeks after the completion of therapy. Replete magnesium with oral or IV supplements as indicated.	

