7. Hematology: CBC with differential including Hgb, and platelet count. Serum chemistries will include a complete metabolic panel (ie, BUN, creatinine, sodium (Na), potassium (K), Chloride (Cl), Bicarbonate (CO2), glucose, calcium (Ca), albumin, total protein, total bilirubin, ALT, AST, and alkaline phosphatase) + magnesium (Mg) and phosphorus.
8. Thyroid function test: TSH and free T3/T4 should be assessed prior to initiating study treatment and performed every 6 weeks +/- 3 days during study treatment and at the end of treatment. ACTH, amylase and lipase should be measured at baseline (pre-study) and

- then on D1 of each cycle. CEA should be measured pre-study and then on D1 of each cycle.
9. Please note all subjects should receive prophylaxis for panitumumab-associated rash with a tetracycline antibiotic (like doxycycline or minocycline) and continue for at least the duration of the first cycle of study combination treatment (i.e., 6 weeks), as described in section 4.5.1
  10. Ipilimumab dosing will be halted and will not be given if the triple combination is determined to be unsafe during the safety run-in period (Cohort 1). If this is the case then subjects will be dosed with panitumumab and nivolumab in (Cohort 2) as described in section 4.3.2
  11. Fixed paraffin-embedded blocks or slides from the original diagnostic specimen or from a metastatic or recurrent site must be requested for subjects at baseline. Subjects with inadequate archival specimens must undergo a mandatory biopsy prior to initiating study medications.
  12. Blood samples will be collected for correlative studies on D1 of each cycle prior to dosing, and at the end of treatment visit.
  13. Stool specimen should be collected +/- 7 days from C3D1.
  14. We will collect fresh on-treatment biopsies (optional) in consenting patients for correlative studies in up to 15 patients. The on-treatment biopsy will be performed during cycle 1 on or between days 28 and 35.

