## 6.4 Post-Treatment/Follow-up Assessments

### 6.4.1 End of treatment

Focused history and physical examination (including weight)

ECOG Performance Status (see appendix 11.1)

Laboratory evaluations:

- Hematology: CBC with differential
- Complete Metabolic Panel (plus Mg and Phosphorus)
- TSH/Free T3/Free T4
- ACTH/Amylase/Lipase
- CEA
- Serum or urine pregnancy test in women of childbearing potential
- Blood sample for correlative studies

Concomitant medication(s): All concomitant medications will be recorded.  
Toxicity evaluation: Use NCI CTCAEv4.03 for notation of any baseline toxicity.  
**Note**: Subjects who experienced a grade 3 or 4 event or SAE during the treatment phase will be contacted every 2 weeks until the event is resolved or deemed irreversible by the investigator.

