### 6.4.2 30-day follow up

Focused history and physical examination (including weight)

Laboratory evaluations:

- Serum or urine pregnancy test in women of childbearing potential

Concomitant medications

Toxicity evaluation: Use NCI CTCAEv4.03 for notation of any baseline toxicity.  
**Note**: Subjects who experienced a grade 3 or 4 event or SAE during the treatment phase will be contacted every 2 weeks until the event is resolved or deemed irreversible by the investigator.

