#### 6.4.4 Long-term follow up

Subsequent long-term follow-up visits should occur per standard of care, defined as every 90 days thereafter (+/- 15 days) for up to 3 years or until death (whichever is first) and may be conducted via telephone, medical record check, and/or via clinic visit. These visits will be limited to history of any subsequent cancer treatments, an assessment of any SAE's considered to be possibly or probably related to study treatment until resolution, and survival status.

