## **7.2 Documentation of non-serious AEs or SARs**

For non-serious AEs or SARs, documentation must begin from day 1 of study treatment and continue through the 100-day follow-up period after treatment is discontinued.

Collected information should be recorded in the electronic Case Report Forms (eCRF) for that subject. Please include a description of the event, its severity or toxicity grade, onset and resolved dates (if applicable), and the relationship to the study drug. Documentation should occur at least monthly.

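### Calcium and magnesium monitoring for up to 8 weeks after therapy (4.4.1) has no scheduled test after End of Treatment in 6.1 or 6.4

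*Combined protocol and SAP*

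**What the plan says.** The Warnings row of the panitumumab table in section 4.4.1 asks sites to monitor for hypomagnesemia and hypocalcemia before the first dose, "periodically during panitumumab treatment, and for up to 8 weeks after the completion of therapy", and to replace magnesium as needed. Section 5.1.7 lists electrolyte depletion among the drug's adverse events and refers sites to 4.4.1 for management.

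The schedule measures these electrolytes only in the serum chemistry panel. Footnote 7 of the Time and Events Table (6.1) includes calcium in that panel and ends its list of analytes with "alkaline phosphatase) + magnesium (Mg) and phosphorus". The panel is marked at pre-study, at each treatment day and at End of Treatment, where 6.4.1 lists "Complete Metabolic Panel (plus Mg and Phosphorus").

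The later contacts are as follows:

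- **30-day visit.** Footnote 3 of 6.1 states: "The 30-day (+/- 7 days) follow up visit after stopping study treatment should be performed to check for ongoing toxicity". Section 6.4.2 includes a physical examination, so the visit is in person. Its only laboratory entry is "Serum or urine pregnancy test in women of childbearing potential".
- **100-day contact.** Footnote 3 says "subjects should be contacted by telephone at approximately 100 days (+/- 7 days) after discontinuing study treatment". Section 6.4.3 lists survival and toxicity only.
- **Long-term follow-up.** Section 6.4.4 says "These visits will be limited to history of any subsequent cancer treatments", together with related serious events and survival status.

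For non-serious adverse events, section 7.2 says "documentation must begin from day 1 of study treatment and continue through the 100-day follow-up period after treatment is discontinued".

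**The concern.** The before-treatment and during-treatment parts of the 4.4.1 instruction are scheduled. The after-treatment part is not. A site that works from 6.1 and 6.4 will draw no calcium or magnesium once the End of Treatment visit is over.

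Low magnesium and low calcium are laboratory diagnoses. They may cause no symptoms that a history or examination would bring out, and replacement cannot be started without a result. The protocol keeps documenting adverse events through the 100-day follow-up, yet no scheduled contact after End of Treatment includes the test that would reveal this one. Detection then depends on each site's habits, in a multicenter trial. What is at stake is the safety of individual subjects and, to a small degree, the completeness of the adverse event record.

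**Working it through.** The plan states no figure to reproduce here. The check sets the instruction beside the schedule and then works out the days.

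**1. Where calcium and magnesium are scheduled.** The serum chemistry row in 6.1 has 11 marks: 1 pre-study + 9 treatment-day columns + 1 End of Treatment. The 30-day, 100-day and long-term columns are blank, and 6.4.2 to 6.4.4 agree with the table. Treatment days are 1, 15 and 29 of a 42-day cycle, so on treatment there is one draw every 14 days. After End of Treatment there are none.

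**2. The window.** 8 weeks × 7 = 56 days after completion of therapy.

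**3. The follow-up contacts, counted from stopping treatment.**

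- 30-day visit: 30 ± 7 gives days 23 to 37, wholly inside the window.
- 100-day call: 100 ± 7 gives days 93 to 107. The earliest date is 93 − 56 = 37 days past the window.

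**4. The window counted from the last panitumumab dose.** Let L be the number of days from that dose to End of Treatment, taken as the day treatment stops. L has to be assumed, because 6.1 sets no interval. The days left with no scheduled test are 56 − L, and the 30-day visit falls on days L + 23 to L + 37.

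| L (days) | Situation | Untested days, 56 − L | 30-day visit, days after last dose |
|---|---|---|---|
| 0 | End of Treatment on the day of the last dose | 56 | 23 to 37 |
| 14 | Stopped at the Cycle 3 Day 1 scan after a Day 29 dose | 42 | 37 to 51 |
| 42 | Stopped after a long interruption | 14 | 65 to 79 |

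The whole visit interval lies inside the window when L + 37 ≤ 56, that is, when L ≤ 19. At L = 42 the visit falls outside the window, but the End of Treatment panel is itself drawn on day 42, inside it.

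**5. What a panel at the 30-day visit would do.** Taken at its nominal date with L = 0, it tests at day 30 and leaves 56 − 30 = 26 days to the end of the window. With L = 14 it tests at day 14 + 30 = 44 and leaves 56 − 44 = 12 days.

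**The case against.** The strongest reply is that 4.4.1 is itself operative text. Section 9.5 requires the study to be run as the protocol describes, and a blank cell in 6.1 does not cancel an instruction elsewhere. The 8 weeks are a ceiling with no stated frequency, so a locally ordered test would satisfy it. This is fair: the obligation exists, and what is missing is its place in the schedule. But some monitoring after therapy is clearly intended, and the documents that sites use to plan visits provide none.

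Several points narrow the gap, and they stand:

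- If only panitumumab stops and nivolumab continues, chemistry continues every 2 weeks and covers the window.
- The End of Treatment panel can fall inside the window when it follows the last dose. That shortens the gap without closing it in the cases tabulated above.
- Footnote 3 of 6.1 follows events of grade 2 or higher, and serious events, that are ongoing at End of Treatment. Sections 6.4.1 to 6.4.3 add contact every 2 weeks after a grade 3 or 4 or serious event on treatment. These rules follow known problems. They do not detect depletion that is new, or that was grade 1 and is worsening without symptoms.

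The note under 3.1.8 also limits which laboratory changes count as adverse events, so 7.2 alone does not prove an intent to record the mildest shifts. That is right, but 4.4.1 asks for the monitoring in its own terms, and 7.3.3 asks for documentation of laboratory abnormalities that need corrective therapy.

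Finally, the documents give no rate or onset time for electrolyte depletion after panitumumab. The day counts measure uncovered calendar time and do not estimate risk.

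**Conclusion.** The concern holds. The protocol asks for electrolyte monitoring for up to 8 weeks after therapy and schedules no calcium or magnesium test after End of Treatment, although an in-person toxicity visit falls within that period. For subjects who stop all study treatment, the uncovered time is 56, 42 or 14 days for L of 0, 14 or 42. These figures rest on the assumed L and on counting from the last panitumumab dose. Counted from stopping treatment, the 30-day visit is always inside the window.

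This is an inconsistency between the safety instruction and the visit schedule, and it should be corrected. It does not touch the response analysis, the sample size or the stopping rules, and it would rarely change the grade 3 and 4 toxicity tables.

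**What to change.** Add the existing serum chemistry panel, with magnesium, to the 30-day column in 6.1 and to the laboratory list in 6.4.2. Add a cross-reference there to 4.4.1, stating that any further calcium and magnesium checks up to week 8 are done locally as clinically indicated.

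The cost is one routine blood panel per subject at a visit that already takes place, plus an edit to two sections. No extra visit is needed.
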